2.7.2 Laboratory data

Evening plasma cortisol will be summarized by visit. The maximum evening plasma cortisol post first dosing (i.e. post baseline value) will be summarized. The changes from baseline will also be summarized by visit.

All laboratory data will be listed with abnormal values flagged.

Baseline laboratory data is defined as the assessment taken 30 minutes pre-dose at Day 1. If this assessment is missing or not confirmed to be pre-dose, the last value taken at the screening Visit 2 or at an unscheduled visit before the first administration of study drug will be used for baseline. Otherwise, the baseline laboratory data will be set to missing.

All data will be included in the analysis regardless of rescue medication usage. Laboratory data measured more than 7 days after last inhalation of study drug is regarded as post-treatment data and will not be summarized, only listed.

The following analyses will be performed:

- absolute values and change from baseline summarized with standard descriptive statistics for continuous laboratory parameters by visit and time point
- frequency table of results for categorical laboratory parameters by visit and time point
- shift tables relative to the normal reference ranges summarizing the change from baseline to post-baseline by visit and time point for each continuous laboratory parameter
- shift tables from baseline to post-baseline by visit and time point for categorical laboratory parameters
- the number and percentage of patients with newly occurring or worsening laboratory abnormalities meeting the clinically notable criteria (see [Section 5.3](#) in this document for definition of notable values) summarized by laboratory parameter, scheduled post-baseline visit and time point and additionally at any time on treatment considering all post-baseline data from scheduled, unscheduled and premature discontinuation visits

The by-visit/time point summaries will include the worst case post-baseline values (determined from all post-baseline data even if from unscheduled and premature discontinuation visits, if not measured more than 7 days after last dose). To determine the worst case, the direction of interest (maximum and/or minimum value) is tabulated for

hematology and biochemistry parameters in [Section 5.3](#). For continuous urinalysis parameters the direction of interest is always "High" (maximum value).

For a patient to meet the criterion of a newly occurring clinically notable value, the patient needs to have a baseline value that is not clinically notable for that parameter. For a patient to meet the criterion of a worsening clinically notable value, the patient needs to have a baseline value that is clinically notable and also have a worse post-baseline value. For patients with missing baseline value, any post-baseline notable value will be considered as newly occurring.

Furthermore, the number and percentage of patients with newly occurring or worsening abnormalities in liver function tests (LFT) at any time post-baseline will be summarized based on the following criteria:

- **Notable liver function test values**

Criterion
ALT > 3 x the upper limit of normal range (ULN) ALT > 5 x ULN ALT > 8 x ULN ALT > 10 x ULN ALT > 20 x ULN
ALT or AST > 3 x ULN ALT or AST > 5 x ULN ALT or AST > 8 x ULN ALT or AST > 10 x ULN ALT or AST > 20 x ULN
Total bilirubin > 1 x ULN Total bilirubin > 1.5 x ULN Total bilirubin > 2 x ULN Total bilirubin > 3 x ULN
ALP > 1.5 x ULN ALP > 2 x ULN ALP > 3 x ULN ALP > 5 x ULN
ALT or AST > 3 x ULN and total bilirubin > 1.5 x ULN ALT or AST > 3 x ULN and total bilirubin > 2 x ULN ALT or AST > 5 x ULN and total bilirubin > 2 x ULN ALT or AST > 8 x ULN and total bilirubin > 2 x ULN ALT or AST > 10 x ULN and total bilirubin > 2 x ULN ALT or AST > 20 x ULN and total bilirubin > 2 x ULN
ALP > 3 x ULN and total bilirubin > 2 x ULN ALP > 5 x ULN and total bilirubin > 2 x ULN
ALT or AST > 3 x ULN and Total Bilirubin > 2 x ULN and ALP ≤ 2 x ULN (Hy's law)
ALT or AST > 3 x ULN and (nausea or vomiting or fatigue or general malaise or abdominal pain or (rash and eosinophilia))*

ALT = alanine aminotransferase, AST = aspartate aminotransferase, ALP = alkaline phosphatase

* Based on the signs/symptoms information as recorded on the liver events eCRF, not the adverse events eCRF.

When a criterion contains multiple laboratory parameters, the criterion will only be considered to have been met when all conditions occur at the same time (i.e., within the same sample). A case where all criteria are met at a post-baseline time point will be considered as newly occurring if the criteria are not met at baseline and will be considered as worsening if the criteria are met at baseline and at least one component is worsening from baseline irrespective of whether the other(s) are better.

Listings of all patients with notable laboratory values and also with clinically notable LFT values will be provided.

2.7.3 Other safety data

2.7.3.1 ECG and cardiac imaging data

Data from the ECG (including ventricular rate, QT interval, RR interval, PR interval, QRS duration, Fridericia's QTc and Bazett's QTc) will be summarized at 30 min pre-dose, and at 30 min post-dose (at selected visits only).

Furthermore, an overall interpretation of the central cardiologist will be provided as well as a specification of abnormal findings. For qualitative assessments, if multiple ECG values were taken, the worst case will be chosen for all summaries.

ECG data measured more than 7 days after last inhalation of study drug is regarded as post-treatment data and will not be summarized, only listed. All data will be included in the analysis regardless of rescue medication usage.

Baseline ECG is defined as ECG measured 30 minutes prior to the first dose of study drug on Day 1. If it is missing (or not confirmed to be pre-dose), then the last assessment taken at the screening Visit 2 or at an unscheduled visit before the first administration of study drug will be used. Otherwise, the ECG baseline will be set to missing without imputation.

QTc will be calculated from the QT interval and RR (in seconds) by two methods:

1. using Fridericia's formula: $QTcF = QT / \sqrt[3]{RR}$, where $\sqrt[3]{}$ denotes the cube root
2. using Bazett's formula: $QTcB = QT / \sqrt{RR}$

The following analyses will be performed:

- absolute values and change from baseline summarized by parameter, visit and time point
- the number and percentage of patients with newly occurring or worsening notable QTcF/QTcB values (see below for definition of notable values) summarized by scheduled post-baseline visit and time point and additionally at any time on treatment considering all post-baseline data from scheduled, unscheduled and premature discontinuation visits
- frequency table of results for overall ECG interpretation (normal, abnormal) by visit and time point and with shift tables from baseline to the worst interpretation during treatment
- the number and percentage of patients with ECG abnormalities summarized by evaluation type, abnormality finding, visit and time point. In addition, the number and percentage of patients with newly occurring or persistent/recurrent ECG abnormalities at any time point over the treatment period (considering all post-baseline data from scheduled, unscheduled and premature discontinuation visits) will be summarized by evaluation type and abnormality finding

The by-visit/time point summaries will include the maximum QTcF/QTcB and maximum ventricular rate (even if from post-baseline unscheduled and premature discontinuation visits, if not measured more than 7 days after last dose).

The same approach as for notable laboratory values will be used to define a newly occurring notable QTcF/QTcB value and a worsening notable QTcF/QTcB value.

A listing of all patients with notable QTcF/QTcB values and changes will be provided.

The following table shows the clinical notable criteria for QTcF/QTcB.

Clinical notable criteria for QTcF and QTcB

ECG parameter (unit)	Clinically notable range
Notable value considering newly occurring or worsening cases	
QTc (ms)	> 450 (male)
QTc (ms)	> 460 (female)
QTc (ms)	> 500
Categories used for the change from baseline	
QTc	30 – 60
QTc	> 60

2.7.3.2 Vital signs

Vital signs measurements include systolic and diastolic blood pressure (SBP and DBP), and pulse rate.

Vital signs data measured more than 7 days after last inhalation of study drug are regarded as post-treatment data and will not be summarized, only listed. All data will be included in the analyses regardless of rescue medication use.

Baseline vital signs are defined as the assessment taken 30 minutes pre-dose at Day 1. If this assessment is missing or not confirmed to be pre-dose, the last value taken at the screening Visit 2 or at an unscheduled visit before the first administration of study drug will be used for baseline.

The following analyses will be performed:

- absolute values and change from baseline summarized by parameter, visit and time point
- the number and percentage of patients by parameter, visit and time point with
 - pulse rate < 40 bpm, 40 – 90 bpm, and > 90 bpm
 - SBP < 90 mmHg, 90 – 140 mmHg, and > 140 mmHg
 - DBP < 50 mmHg, 50 – 90 mmHg, and > 90 mmHg
- the number and percentage of patients with newly occurring or worsening notable vital signs values (see below for definition of notable values) summarized by parameter, scheduled post-baseline visit and time point and additionally at any time on treatment considering all post-baseline data from scheduled, unscheduled and premature discontinuation visits

The by-visit/time point summaries will include the maximum and minimum post-baseline SBP, DBP, and pulse rate values (even if from post-baseline unscheduled and premature discontinuation visits, if not measured more than 7 days after last dose).

The same approach as for notable laboratory values will be used to define a newly occurring notable vital sign value and a worsening notable vital sign value.

A listing of all patients with notable vital sign values and changes will be provided.

The following table shows the clinical notable criteria for vital signs.

Clinical notable criteria for vital signs

Vital sign parameter (unit)	Lower bound of clinically notable range	Upper bound of clinically notable range
Notable value considering newly occurring or worsening cases		
Systolic blood pressure (mmHg)	< 75	> 200
Diastolic blood pressure (mmHg)	< 40	> 115
Pulse rate (bpm)	< 40	> 130
Notable change from baseline		
Systolic blood pressure (mmHg)	≤ 90 and decrease from baseline by ≥ 20	≥ 180 and increase from baseline by ≥ 20
Diastolic blood pressure (mmHg)	≤ 50 and decrease from baseline by ≥ 15	≥ 105 and increase from baseline by ≥ 15
Pulse rate (bpm)	≤ 50 and decrease from baseline by ≥ 15	≥ 120 and increase from baseline by ≥ 15

2.8 Pharmacokinetic endpoints

Not applicable.

2.9 PD and PK/PD analyses

[figure not shown]
Not applicable.

[figure not shown]
2.10 Patient-reported outcomes

Not applicable.

[figure not shown]
2.11 Biomarkers

Not applicable.

2.13 Interim analysis

The cut-off date for each patient is defined as the Visit 107 date or study discontinuation date prior to Visit 107. All protocol specified analyses will be performed for all data on or prior to this cut-off date.

3 Sample size calculation

Since asthma is a chronic disease, and QMF149 is expected to be administered over a long period, safety in long-term treatment needs to be confirmed. “Regarding sample size and treatment period required to assess safety at the clinical study stage of a new drug anticipated to be administered for a non-fatal disease over a long period” (Notification No. 592 of the Pharmaceuticals and Cosmetics Division, Pharmaceutical Affairs Bureau, MHLW, dated 24-May 24, 1995), this notification requires to collect safety data of at least 100 patients who receive the drug over one year. CQVM149B2301 and 2302 study were planned to collect

efficacy and safety data of about 41 Japanese Asthma patients exposed to QMF149. Therefore this study, CQVM149B1305, is designed to obtain safety data of approximately 59 Japanese asthma patients exposed to QMF149. Since a 25% screening failure rate and a 10% dropout rate are expected, approximately 88 patients will need to be screened in order to collect approximately 66 patients who enter the treatment epoch and to collect a total of approximately 59 completed patients.

4 Change to protocol specified analyses

No change from protocol specified analysis is made.

5 Appendix

5.1 Imputation rules

No imputation is planned in this study.

5.2 AEs coding/grading

Refer to the AEs analyses described in [Section 2.5](#) in this document.

5.3 Laboratory parameters derivations

Direction of interest and definition of clinically notable values

The following table shows the direction of interest when analyzing worst case values in form of maximum and/or minimum post-baseline values. If the direction of interest is given as "High" the maximum value will be calculated and used as worst value, if the direction is given as "Low" the minimum value will be taken, and if it is given as "Low and high", both the minimum value and the maximum value will be calculated and presented in summary tables.

Direction of interest for worst case value for laboratory parameters

Laboratory Parameter	Direction of interest for worst case value
A. Hematology	
Hemoglobin	Low
Hematocrit	Low
Erythrocytes	Low
Leukocytes	Low and high
Basophils	High
Eosinophils	High
Lymphocytes	Low and high
Monocytes	High
Neutrophils	Low and high
Platelets	Low and high
B. Chemistry	
Albumin	Low
Alkaline Phosphatase	High
ALT/SGPT	High
AST/SGOT	High
Bilirubin Total	High
Blood Urea Nitrogen (BUN)	High
Creatinine	High
Glucose	Low and high
Gamma GT	High
Potassium	Low and high
Sodium	Low and high
Magnesium	Low and high
Uric acid	High
Plasma cortisol	Low and high

The following table shows the criteria for clinically notable laboratory values. Not all parameters have notable criteria defined.

Clinical notable criteria for selected laboratory tests

Laboratory parameter (unit)	Lower bound of clinically notable range	Upper bound of clinically notable range
Hematology		
Hematocrit (v/v)		
Male	0.37	-
Female	0.32	-
Hemoglobin (g/L)		
Male	115	-
Female	95	-
Platelets (x10 ⁹ /L)	75	700
Leukocytes (x10 ⁹ /L)	2.8	16.0
Chemistry		
Albumin (g/L)	25	-
Alkaline Phosphatase (U/L)	-	3 x ULN
ALT/SGPT (U/L)	-	3 x ULN
AST/SGOT (U/L)	-	3 x ULN
Bilirubin Total (µmol/L)	-	34.2
BUN (mmol/L)	-	9.99
Creatinine (µmol/L)	-	176.8
Glucose (mmol/L)	2.78	9.99
Gamma GT (U/L)	-	3 x ULN
Potassium (mmol/L)	3	6
Magnesium (mmol/L)	0.51	1.07

v = volume, ULN = upper limit of normal

5.4 Statistical models**5.4.1 Primary analysis**

Not applicable.

5.4.2 Key secondary analysis

Not applicable.

5.5 Rule of exclusion criteria of analysis sets

The following protocol deviations will be considered as major and will lead to exclusion of patients from the FAS or the Safety Set:

- Patient received study drug but not intended to enter in the treatment epoch of this study (excludes from FAS)

Note: The list will be completed when the major PDs are defined and will be updated shortly before database lock.

Protocol deviations will lead to patient classification into the analysis sets as follows:

Analysis set exclusions based on population codes

Analysis set	Population codes that cause a subject to be excluded
SAF	2, 3
FAS	1, 3

Population code text

Population Code	Population code - text
0	INCLUDE IN EVERYTHING
1	EXCLUDE FROM FULL ANALYSIS SET (FAS)
2	EXCLUDE FROM SAFETY
3	EXCLUDE FROM FAS AND SAFETY

Note that the population codes will be derived in the analysis datasets and are not part of the source data.

Unless otherwise stated, summary tables, figures and listings will be on all subjects included in the analysis set under consideration.

Protocol deviations that cause subjects to be excluded

Deviation ID	Description of Deviation	Exclusion in Analyses
TRT01	Patient was entered treatment epoch but no study drug was taken	Excluded form FAS and Safety Set analysis
TRT02	Patient received wrong treatment or expired drug	Excluded form FAS analysis

6 Reference

Not applicable.

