### **9.1 Analysis sets**

The Safety Set will consist of all patients who received at least one dose of study medication during this study.

Full Analysis Set (FAS) will consist of all patients who entered in this study and received at least one dose of study medication during this study.

Note that the Safety Sets and FAS are the same except that the Safety Set allows the inclusion of patients who are not intended to enter in this study but received study drug in error.

The Safety Set will be used in the analysis of all safety variables. The efficacy analysis population will be the FAS.

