2.2 Analysis sets

The Safety Set will consist of all patients who received at least one dose of study medication during this study. The Safety Set will be used in the analysis of all safety variables.

Full Analysis Set (FAS) will consist of all patients who entered in the treatment epoch of this study and received at least one dose of study medication during this study. The efficacy analysis will be based on FAS.

Note that the Safety Set and FAS are the same except that the Safety Set allows the inclusion of patients who are not intended to enter in the treatment epoch of this study but received study drug in error.

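### SAP 5.5 (TRT02) removes from the Full Analysis Set patients whom Protocol 9.1 and SAP 2.2 include, and SAP Section 4 declares no change

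*SAP*

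**What the plan says.** Protocol 9.1 defines the set: "Full Analysis Set (FAS) will consist of all patients who entered in this study and received at least one dose of study medication". SAP 2.2 narrows entry to the treatment epoch and otherwise keeps the rule: "all patients who entered in the treatment epoch of this study and received at least one dose of study medication". Both documents add a note on how the two analysis sets differ. In the SAP it begins "the Safety Set and FAS are the same except that the Safety Set allows the inclusion of patients" and goes on to name one group, those who were not meant to enter but were given study drug by mistake.

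SAP 5.5 then gives rules for leaving patients out, in two places:

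- A bullet list of major deviations has one item, the patient dosed without being meant to enter, who is left out of the FAS.
- A deviation table has two rows. TRT01, "Patient was entered treatment epoch but no study drug was taken", removes the patient from both sets. TRT02, "Patient received wrong treatment or expired drug", removes the patient from the FAS only.

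A note under the bullet says "The list will be completed when the major PDs are defined and will be updated shortly before database lock". SAP Section 4 says "No change from protocol specified analysis is made".

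**The concern.** TRT02 is a second route out of the FAS that the definition does not contain. It has no qualifier for number of doses, duration, or whether valid QMF149 was also taken. Read literally, one expired capsule in 52 weeks removes a patient from every efficacy summary: FEV1, FVC, PEF, rescue use and ACQ-7. Two programmers, one working from SAP 2.2 and the other from SAP 5.5, would build different efficacy populations from the same data.

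The exclusion also acts on something that happens after entry, in an open-label trial, and the protocol's FAS does not permit it. If it is intended, it is a change from the protocol and Section 4 should say so.

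**Working it through.** **Text comparison.** Four kinds of patient, set against the definition (Protocol 9.1, SAP 2.2) and against SAP 5.5:

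| Patient | FAS by definition | FAS by SAP 5.5 | Conflict |
|---|---|---|---|
| Entered, no study drug taken | Out | Out (TRT01) | No |
| Dosed, not meant to enter | Out | Out (bullet) | No |
| Entered, took only a non-study product | Out (no dose of study drug) | Out (TRT01 and TRT02) | No |
| Entered, took expired QMF149, or QMF149 and also a wrong product | In | Out (TRT02) | **Yes** |

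The fourth row cannot be removed by arguing that expired drug is not study medication. The Safety Set also requires a dose of study medication, and TRT02 leaves its patients in the Safety Set, whereas TRT01 takes them out of both. The SAP's own coding therefore treats TRT02 patients as dosed. An entered, dosed patient belongs in the FAS.

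**The plan's own numbers.** Protocol 9.8 and SAP Section 3: 100 − 41 = 59 completers; 59 / 0.90 = 65.6, so 66 treated; 66 / 0.75 = 88 screened. These reproduce and TRT02 does not affect them. They supply two denominators: 66 treated, and about 59 at Week 52 (66 × 0.90 = 59.4). The second applies because missing data are not imputed (SAP 2.6.3), off-treatment measures are not used (SAP 2.6.1), and early-discontinuation visits are only listed, for efficacy (SAP 2.1.1).

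**Size, under assumptions.** The documents give no TRT02 frequency and no expected responder rate. Assumed: k = 0 to 3 cases, all responders or all non-responders (the worst case), and an ACQ-7 responder rate of about 40% to 70%, that is 26 to 46 of 66, or 24 to 41 of 59.

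- Removing k non-responders changes the rate from r/n to r/(n − k). This gives the largest shift at the top of the assumed range.
- If each removed patient lies 1 SD from the mean on the same side, the mean shifts by k/(n − k) SD.

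| k | Largest shift, n = 66 | Largest shift, n = 59 | Mean shift, n = 66 | Mean shift, n = 59 |
|---|---|---|---|---|
| 0 | 0 | 0 | 0 | 0 |
| 1 | 46/66 to 46/65: 1.1 points | 41/59 to 41/58: 1.2 points | 0.015 SD | 0.017 SD |
| 2 | 46/66 to 46/64: 2.2 points | 41/59 to 41/57: 2.4 points | 0.031 SD | 0.035 SD |
| 3 | 46/66 to 46/63: 3.3 points | 41/59 to 41/56: 3.7 points | 0.048 SD | 0.054 SD |

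A single case can matter less: removing one responder takes 41/59 to 40/58, or 69.5% to 69.0%, a shift of 0.5 points. A TRT02 patient who already lacks Week 52 data changes nothing at Week 52. The effect on the primary adverse event count is none (SAP 2.5.1 uses the Safety Set).

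**The case against.** The strongest reply is that nothing of consequence follows. The FAS supports descriptive summaries only, no test or threshold depends on it, SAP 2.3.1 tabulates and lists every exclusion with its reason, and there may be no TRT02 case at all. All of that stands, and it is why the point is minor. It does not make the two rules agree.

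A second reply is that the exclusion list is openly unfinished. The note says the list will be completed and updated. It does not say that rows already in the table are provisional, or that a later list may override the definition in SAP 2.2.

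A third is that the SAP never defines wrong treatment. With one drug, one dose and no control (Protocol 5.1.1), it might mean a wrong kit with identical contents, a different product alone, or a mixture. This has force: the expired-QMF149 case is the plain one, and the wrong-product case depends on QMF149 also having been taken. A patient who took only a non-study product also meets both table rows, which differ on the Safety Set. That overlap needs tidying, but SAP 2.2 settles it, since such a patient had no dose of study drug and is in neither set.

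Fourth, the cap of 3 cases is a choice. With 5 cases on 59 patients the largest shift is 41/59 to 41/54 (69.5% to 75.9%, 6.4 points) and the mean shift is 5/54 = 0.093 SD. Having one arm and no control drug makes wrong-treatment cases less likely, but says nothing about expiry. The FEV1 denominator may also fall below 59, because values close to rescue or systemic corticosteroid use are set to missing (SAP 2.6.2). The figures are illustrations, not bounds.

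**Conclusion.** The concern holds. For an entered patient who took expired QMF149, or QMF149 and also a wrong product, TRT02 contradicts the FAS definition in both documents, and the no-change statement in SAP Section 4 is then incorrect. The rest of TRT02 does not conflict.

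Severity is minor. The effect is confined to secondary efficacy summaries and is zero if no case occurs. Under the assumptions above it is a few percentage points at most on the ACQ-7 responder rate and about 0.05 SD on a mean change. The textual conflict needs none of those assumptions; only its size does.

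The bullet and the table in SAP 5.5 have no item in common. They can be read as complementary, so this is alignment work and not a second contradiction.

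**What to change.** In SAP 5.5:

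- Remove TRT02 as a reason for FAS exclusion where the patient entered and took one or more doses of study drug. Keep it as a reported protocol deviation. SAP 2.3.1 already tabulates deviations, and Protocol 7.5 already collects treatment errors in the dose administration record. A sensitivity summary without these patients is optional.
- List the same exclusions in the bullet and the table: no study drug taken (both sets), and dosed but not meant to enter (FAS only).
- State that the exclusion rules are fixed before the lock for the Week 26 interim analysis, which runs all protocol-specified analyses, and that they may not override SAP 2.2.

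If the sponsor does want the TRT02 exclusion, it should instead write it into the FAS definition in SAP 2.2 and declare the change in SAP Section 4.

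Either route costs SAP wording only. Conduct, data collection and sample size are unaffected.
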